6.2 IMPORTANT PROTOCOL DEVIATIONS

Data discrepancies and deviations from the CTP will be identified for all patients in the database (i.e., enrolled patients). Consistency check listings (for identification of violations of time windows) and a list of protocol deviations will be provided to be discussed at the RPM/DBLM/MQRM. At meetings, it will be decided whether a discrepant data value can be used in analyses or whether it must be queried in the clinical database. Each protocol deviation must be assessed to determine whether it is an iPD. For definition of iPDs, and for the process of identification of these, refer to the BI reference document "Identify and Manage Important Protocol Deviations (iPD)" (2).

Handling of iPDs in the analysis is included in the DV domain specifications and stored within the TMF in EDMS.

6.3 SUBJECT SETS ANALYSED

The following analysis sets will be defined for this trial:

[figure not shown]
- **Enrolled set (ES)**
This patient set includes all patients who signed informed consent. It will be used for display of patient disposition.
- **Safety analysis set (SAF)**
This patient set includes all randomized patients who received at least one dose of study drug. It will be the main analysis set for presentation of safety. In addition, this set will be used for display of baseline and demographic characteristics, and patients with iPDs.
- **Full analysis set (FAS)**
This patient set includes all patients in the SAF who had a baseline measurement and at least one post-baseline measurement for the secondary endpoint, EASI Total Score. It will be the main analysis set for presentation of efficacy results.

The discussion of all exceptional cases and problems and the decisions on the allocation of patients to populations will be made at latest at the DBLM.

Table 6.3: 1 Subject sets analysed

Class of endpoint	Subject set		
	ES	SAF	FAS
Primary and key secondary endpoints			X
(other) Secondary and further endpoints			X
Safety endpoints & treatment exposure		X	
Patients disposition	X		
Demographic/baseline endpoints		X	

Note that the number of subjects with available data for an endpoint may differ. For details, see section “Handling of missing data”.

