1.4.2 Risks

There are no identified or potential safety risks for BI 655130, based on the toxicology programme or any clinical trials conducted for this product to date (Refer to [Section 1.2](#)). No other IL-36 receptor antagonist is currently approved, providing information on identified risks in molecules of this class.

Currently there are no data available to suggest interactions of BI 655130 with other drugs [[c03320877-06](#)]. Since the drug exposure in this trial is expected to be lower than in the parent trial (1368-0032), there is a risk that some patients will lose response. Rules for discontinuation for these patients are outlined in [Section 3.3.4.1](#).

The risks shown in the table below are hypothetical in nature; these are derived from general safety considerations of immunomodulatory drugs.

In order to protect the patient's safety during conduct of this trial, an independent Data Monitoring Committee has been established for the periodic review of clinical trial safety data.

Table 1.4.2:1 Study Risks

Hypothetical risks of clinical relevance for this trial	Summary of data, rationale for the risk	Mitigation strategy
Investigational Medicinal Product		
Drug Induced Liver Injury (DILI)	Rare but severe event, thus under constant surveillance by sponsors and regulators.	Timely detection, evaluation, and follow-up of laboratory alterations in selected liver laboratory parameters to ensure patients' safety. See Section 5.2.6 (AESI)

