7.2 PLANNED ANALYSES

7.2.1 General considerations

The efficacy analyses will be performed for the Full Analysis Set (FAS) that includes all patients who entered the study, received at least one dose of treatment, had a baseline measurement, and at least one post-baseline measurement.

All safety analyses will be performed on patients who entered the study and received at least one dose of treatment during the trial. This set of patients is called Safety Analysis Set (SAF).

With regard to efficacy and safety endpoints “baseline” refers to:

1. Baseline for the parent trial – the measurement recorded at randomisation visit (Visit 2) of the parent trial (1368-0032). If the data at Visit 2 is missing, then the data from Visit 1 of the parent trial will be considered baseline.
2. Baseline for the extension trial – the last measurement before the BI655130 treatment intake in this extension trial.

Two separate analyses will be conducted – one including baseline from parent trial and the second including baseline from this extension trial.

Important deviations of the protocol will include key inclusion and exclusion deviations, incorrect medication taken, concomitant use of restricted medications, and any other deviations from the protocol deemed important by the study team.

This is an exploratory trial and sensitivity analyses may need to be done to investigate the effects of potential confounding factors.

Standard statistical parameters (number of non-missing values, mean, standard deviation (SD), median, quartiles, minimum and maximum) of frequency tables (including patient frequencies and percentages) will be calculated where appropriate.

The statistical parameters will be provided for the following groups:

1. By treatment received in the parent trial (1368-0032):
 - Placebo followed by BI655130 treatment
 - Placebo followed by no BI655130 treatment
 - BI655130 followed by BI655130 treatment
 - BI655130 followed by no BI655130 treatment
 - Total
2. By the response achieved at week 16 of the parent trial (1368-0032):
 - Responders – patients who attained at least 75% reduction in EASI score at week 16 compared to baseline during the parent trial
 - Non-responders - patients who attained less than 75% reduction in EASI score at week 16 compared to baseline during the parent trial;
 - Total

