7.3 HANDLING OF MISSING DATA

Every effort will be made to collect complete data at all visits. However, missing data will still occur and approaches to handle this are proposed below.

With respect to safety or continuous efficacy evaluations, it is not planned to impute missing values.

For all binary endpoints (i.e. endpoints that are either 1 (patient responded) or 0 (patient did not respond)), the following rules apply:

- If there are data at visits both before and after the visit with a missing outcome, then impute as responder only if both neighbouring visits also represent a responder;
- Otherwise, impute as a non-responder.

For disease specific protein markers the following handling of data below or above the limit of quantification will be applied:

- Below limit of quantification (BLQ) data will be replaced by 0.5 times the lower limit of the quantification (LLOQ)
- Above limit of quantification (ALQ) data will be replaced by upper limit of quantification (ULOQ), if ULOQs are available. Otherwise, ALQ data will be excluded from the analysis.

Further sensitivity analyses to assess the robustness of the results may be performed and as such will be described in the TSAP.

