6.6.2 Efficacy data

Binary efficacy endpoints

The primary imputation approach for binary endpoints will be No Response Imputation (NRI) described below.

1. If a patient prematurely discontinues study medication administration for any reason, then all data subsequent to the discontinuation will be considered to be missing. The cut-off date to be used is the last dose of study medication administration + 4 weeks (including the extended time windows).
2. For endpoints which are measured at multiple visits, if there are data at visits both before and after the visit with a missing outcome, then impute as success (a responder) only if both neighbouring visits also represent a success (independent of whether the preceding and following observations were selected for analysis based on time windows described in [Section 6.7](#)).

For all patients with a missing visit outcome, it will be imputed as a failure to achieve a response (non-responder).

In addition, for all binary endpoints (i.e., endpoints that are either 1 (patient responded) or 0 (patient did not respond)), frequency tables with observed data will be presented.

Categorical efficacy endpoints with more than two outcomes

Some endpoints or their subscores are categorical with more than two potential outcomes (e.g., IGA, DLQI). As a general rule, imputation will only be applied on the complete score. In case a categorical subscore is analysed separately, no imputation will be applied (only observed data will be analysed).

Continuous efficacy endpoints

For efficacy endpoints which are continuous in nature, no imputation of missing data is planned. Only observed data will be used for analysis.

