7. PLANNED ANALYSIS

All efficacy and safety analyses will be purely exploratory in nature. The following analyses are planned throughout the trial.

- **Status review (at the requested timelines)**

The status reviews will be performed periodically and on demand. The analyses will include all data available at the time of the snapshot. The analyses are planned to be defined for each time point as requests in the CSAP, depending on the requirements.

- **Final analysis (Week 220)**

The analysis of the entire efficacy, safety, PK, and biomarker data collected through the full 220 weeks of follow-up will be performed once all entered patients have completed the trial (up to EoS Visit); at that time point, a final database lock will be done and all data through week 220 will be reported. The majority of biomarkers will be reported outside the CTR.

General Remarks

The format of the listings and tables will follow the BI guideline “Standards for Reporting of Clinical Trials and Project Summaries” [BI-KMED-BDS-HTG-0045] (7) with the exception of those generated for PK.

The individual values of all patients will be listed, including those collected during the off-treatment period. Listings will generally be sorted by country, centre number, patient number and visit (if visit is applicable in the respective listing). AE listings will be sorted by treatment (see [Section 7.8.1](#) below for details).

The following standard descriptive statistical parameters will be displayed in summary tables of continuous variables:

N	number of non-missing observations
Mean	arithmetic mean
SD	standard deviation
Min	minimum
Q1	lower quartile
Median	median
Q3	upper quartile
Max	maximum

The data format for descriptive statistics of concentrations will be identical with the data format of the respective concentrations.

Statistical parameters will be displayed to a defined number of decimal places as specified in the BI guideline “Standards for Reporting of Clinical Trials and Project Summaries” (7).

Tabulations of frequencies for categorical data will include all possible categories and will display the number of observations in a category as well as the percentage (%) relative to the respective treatment. Percentages will be rounded to one decimal place. The category missing will be displayed if and only if there actually are missing values. Percentages will be based on all patients in the respective patient set whether they have non-missing values or not.

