7.5 SECONDARY ENDPOINT(S)

7.5.1 Key secondary endpoint(s)

[figure not shown]
This section is not applicable as no key secondary endpoint has been specified.

7.5.2 (Other) Secondary endpoint(s)

All secondary efficacy endpoints will be analysed descriptively based on the FAS.

For continuous secondary efficacy endpoints (EASI Score and SCORAD Score), standard statistical parameters (as defined in [Section 7](#)) will be presented per group defined in [Section 6.1](#). Both absolute and percent change from baseline will be analysed as an outcome as well as the values recorded at the respective time points.

For binary endpoints (EASI50, EASI75, achieving at least 2-grade reduction from baseline to clear (0) or almost clear (1) in IGA), frequency tables will be provided per group defined in [Section 6.1](#).

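### The FAS leaves out treated patients who have no post-baseline EASI, whom non-responder imputation would count as failures, so EASI50, EASI75 and IGA response rates can only be raised

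*SAP*

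**What the plan says.** SAP 6.3 defines the FAS as patients in the safety set with a baseline and "at least one post-baseline measurement for the secondary endpoint, EASI Total Score". Protocol 7.2.1 is similar but does not name the measure: the patient must have "received at least one dose of treatment, had a baseline measurement, and at least one post-baseline measurement".

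SAP 7.5.2 then states: "All secondary efficacy endpoints will be analysed descriptively based on the FAS". That covers EASI50, EASI75 and the IGA response. The general remarks in SAP 7 fix the denominator: "Percentages will be based on all patients in the respective patient set whether they have non-missing values or not". In SAP 6.1 even the overall total column is defined on the FAS.

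For missing binary outcomes, SAP 6.6.2 makes NRI the primary approach. It starts with early stopping: "If a patient prematurely discontinues study medication administration for any reason, then all data subsequent to the discontinuation will be considered to be missing", with a cut-off four weeks after the last dose. A gap is filled as a response only if both neighbouring visits are responses. Beyond that, "For all patients with a missing visit outcome, it will be imputed as a failure to achieve a response (non-responder". Protocol 7.3 has the same exception and then says: "Otherwise, impute as a non-responder".

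**The concern.** NRI exists so that a patient who stops treatment counts as a failure instead of dropping out of the calculation. It needs no post-baseline value to do this. The FAS definition acts first, however, and removes some of the patients to whom NRI would apply. Two patients who stop at the same time for the same reason can be handled differently: one who comes back for an EASI may count as a non-responder, while one reached only by phone is not counted.

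The trial has one arm and no hypothesis test, so no type I error is at stake. What is at stake is the absolute response rate, which is the efficacy result here.

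Early loss of response is also of real interest. Entry requires a response in the parent trial. Protocol 1.4.2 expects lower exposure than in that trial and accepts that "there is a risk that some patients will lose response". Under protocol 4.2.2.1, use of rescue medication ends trial treatment.

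**Working it through.** The plan gives no response rate, dropout rate or calculated sample size, so there is no figure to reproduce. The check is whether such a patient can arise, which way the effect goes, and how large it could be.

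**Can it arise?**
- The Year 1 flow chart schedules EASI and IGA at V1, then V4 (Week 12), V7, V10 and V13.
- Drug is given at V1, V2 (Week 4) and V3 (Week 8). A patient can therefore have three doses and no scheduled post-baseline EASI.
- Protocol 6.2.3 provides a phone contact for patients who cannot come to the site for EOT and EOS. It collects adverse events and changes in concomitant therapy, so it yields no EASI.

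**Which way does it go?**
- A patient with no post-baseline EASI has no later response on either side of Week 48, so the neighbouring-visit exception cannot apply. NRI would give non-response.
- For IGA this assumes that EASI and IGA are missing together, which is reasonable because they share one row of the flow chart.

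Let N be the treated patients with a baseline value, d those among them with no post-baseline EASI, and r the Week 48 responders.
- Rate on all treated under NRI: r/N.
- Rate on the FAS as written: r/(N-d).
- Ratio: N/(N-d), which is at least 1. The rate rises if d and r are both above zero, and stays at 0% if r is zero.

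**How large?** Protocol 7.5 plans about 40 patients and at most 45. The values of r and d are assumptions.

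| N, r | r/N | d = 1 | d = 2 | d = 4 |
|---|---|---|---|---|
| 40, 12 | 30.0% | 30.8% | 31.6% | 33.3% |
| 40, 20 | 50.0% | 51.3% | 52.6% | 55.6% |
| 40, 28 | 70.0% | 71.8% | 73.7% | 77.8% |
| 45, 22 | 48.9% | 50.0% | 51.2% | 53.7% |

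For example, 20/40 = 50.0% and 20/36 = 55.6%. The factor is 1.026 when 2.5% are excluded, 1.053 at 5% and 1.111 at 10%.

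Results are also split by four parent-treatment sequences and by Week 16 response. In an assumed group of 10 with 5 responders, one exclusion moves 5/10 = 50.0% to 5/9 = 55.6%.

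**The case against.** A reader might infer that the earliest dropouts as a class leave the denominator. The documents do not support that. Flow chart footnote 4 asks every treated patient, including early stoppers, to attend EOT promptly and EOS 16 weeks after the last dose. Protocol 6.2.3 asks sites to make every effort to achieve this. Protocol 6.2.2 asks patients who suspect worsening to come in for an unscheduled visit, and SAP 6.7 assigns unscheduled efficacy measurements to analysis windows. Anyone with an on-site EASI on such an occasion may stay in the FAS and be scored as a failure. The procedure table for EOT and EOS is not in the text available, so whether EASI is done there cannot be confirmed. This objection stands: d is unknown and may be zero.

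A reader might also infer that the excluded patients are mainly those who lost response. That is plausible but not shown. Patients who worsen or need rescue may be the ones most likely to be seen on site, and those reached only by phone may have left for other reasons. The direction of the effect does not depend on this, because it follows from the NRI rule alone.

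Three further points have some force:
- The SAP follows the protocol's post-baseline requirement, so this is a weakness of both documents and not a departure by the SAP.
- A single FAS gives binary and continuous endpoints a common population, so the condition is not without purpose.
- SAP 7 reports the size of each analysis set and lists individual values, so a reader could rebuild r/N. However, the set sizes are tabulated overall only, so for the smaller groups the reader would have to work from the listings.

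**Conclusion.** The point holds in a limited form. A treated patient who is never assessed for EASI after baseline drops out of the responder analyses, although NRI would count that patient as a failure. The exclusion can only raise the three response rates or leave them at 0%, by the factor N/(N-d).

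For 1 to 4 exclusions among 40 treated, at all-treated rates of 30% to 70%, the rise is about 1 to 8 percentage points. At d = 0 it is nil. The counts are illustrative, so one cannot conclude that the reported rates will be inflated, only that the definition allows it and in one direction.

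The SAP also does not say whether an EASI taken after the NRI cut-off, such as one at EOS, is enough to enter the FAS. No responder analysis on all treated patients appears in the text available. This is a minor point in a descriptive trial, but cheap to put right.

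**What to change.** In SAP 6.3 and 7.5.2, for the NRI analyses of EASI50, EASI75 and IGA response, use as denominator all treated patients with a baseline value of the measure concerned, under each of the two baseline definitions. Keep the post-baseline requirement for the continuous endpoints, where only observed data are analysed. Record this as a change from protocol 7.2.1.

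If the sponsor prefers to keep the FAS as the main set, add a sensitivity row on all treated patients with a baseline beside each FAS result, and give the number excluded for lack of a post-baseline EASI in each reported group.

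In either case, state whether an EASI after the NRI cut-off qualifies a patient for the FAS.

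The cost is SAP wording and a little programming, with no new data. The response rates may be slightly less favourable, and binary and continuous efficacy endpoints will have different denominators, which table footnotes should explain.

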7.2.2 Primary endpoint analyses

The primary endpoint is the number of patients with treatment emergent AEs at week 48 and will be a part of the safety analysis (as described in [Section 7.2.5](#)). The primary analysis will be descriptive and will result in frequency table presenting the numbers and percentages of patients with treatment emergent AEs displayed per group as defined in [Section 7.2.1](#) and also by the following subgroups:

- Asian/Non-Asian
- Age groups: <=30 years old/>30 years old

The primary analysis will be performed on the SAF.

[figure not shown]

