- **"Speso 600 mg SC q4w" followed by "no Speso 600 mg SC q4w"** – patients who were randomised to receive active treatment (Speso) in the double-blind period of the parent trial and didn't receive Speso treatment in the open-label period of the parent trial (but didn't discontinue the parent study prematurely)
- **"Overall Total"** – all patients from FAS, regardless of the treatment received in the parent trial.

2. By the response achieved at Week 16 of the parent trial (1368-0032):

- **"Responders"** – patients who attained at least 75% reduction in EASI score at Week 16 compared to baseline during the parent trial
- **"Non-responders"** – patients who attained less than 75% reduction in EASI score at Week 16 compared to baseline during the parent trial
- **"Overall Total"** – all patients from FAS, regardless of the EASI response status at Week 16 in the parent trial.

More details on the technical implementation of these analyses are provided in the ADS Plan of this TSAP.

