7.4.1 Primary analysis of the primary endpoint(s)

The analysis of the primary endpoint will be descriptive in nature and will be a part of the Safety analyses described in detail in [Section 7.8](#).

The primary analysis will be performed on the SAF.

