7.8 SAFETY ANALYSIS

All safety analyses will be performed based on the SAF following BI standards. No hypothesis testing is planned.

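### The SAP's analysis-set table puts the primary endpoint (patients with treatment-emergent AEs at Week 48) on the FAS, while the SAP text and the protocol put it on the SAF

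*SAP*

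**What the plan says.** SAP 5.1 defines the primary endpoint as the number and percentage of patients with treatment-emergent AEs at Week 48 and makes it part of the safety analysis. Four places then name the analysis set.

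- **SAP 6.3, Table 6.3: 1.** The columns are ES, SAF and FAS. The row "Primary and key secondary endpoints" has a single mark, under FAS. A separate row for safety endpoints and exposure is marked under SAF.
- **SAP 7.4.1.** "The primary analysis will be performed on the SAF".
- **SAP 7.8.** "All safety analyses will be performed based on the SAF following BI standards".
- **Protocol 7.2.2.** It also puts the primary analysis on the SAF, as a table of "numbers and percentages of patients with treatment emergent AEs displayed per group as defined in" Protocol 7.2.1. The groups there are parent-trial treatment and Week 16 response, each with a Total that is not restricted to any set.

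SAP 6.1 repeats those groups for descriptive statistics in general but defines the two Overall Total groups as "all patients from FAS, regardless of the treatment received in the parent trial" and "all patients from FAS, regardless of the EASI response status at Week 16 in the parent trial".

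On denominators, the general remarks in SAP 7 say "Percentages will be based on all patients in the respective patient set whether they have non-missing values or not".

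On the SAF itself, SAP 6.3 says "This patient set includes all randomized patients who received at least one dose of study drug". Protocol 7.2.1 asks only that the patient entered the study and received at least one dose, and Protocol 7.4 states that nobody is randomised in this trial.

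**The concern.** The table is where a programmer looks up the population for each output, and for the trial's only primary endpoint it names the wrong one. SAP 5.2.1 and 7.5.1 say there is no key secondary endpoint, so the row governs nothing except the AE endpoint.

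The FAS is the SAF restricted to patients with a baseline and at least one post-baseline EASI. A primary safety result should not depend on whether an efficacy score was obtained. The Year 1 flow chart schedules the first post-baseline EASI at Week 12, so a patient who stops early can have AE data and no EASI. Protocol 6.2.3 provides one route: patients who cannot attend the EOT and EOS visits are telephoned about adverse events and concomitant therapy.

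Such losses may be related to the endpoint. Adverse events can end treatment (Protocol 3.3.4.1), rescue medication ends it (Protocol 4.2.2.1), and worsening of the underlying disease is itself recorded as an AE (Protocol 5.2.6.1.1).

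The Overall Total definitions point the same way. The component groups in SAP 6.1 carry no FAS restriction, so in a safety table the groups could add up to more than their own total.

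**Working it through.** **1. Is the column reading sound?** The table was extracted from PDF, so the position of each mark was checked against every row. Disposition falls under ES, safety and exposure under SAF, demographics and baseline under SAF, and the primary row and the other-secondary row under FAS. All five positions fit together, so a displaced mark in the primary row is an unlikely explanation.

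**2. Which set does each passage give for the primary endpoint?**

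| Passage | Set |
|---|---|
| SAP Table 6.3: 1, primary row | FAS |
| SAP Table 6.3: 1, safety row | SAF |
| SAP 7.4.1 | SAF |
| SAP 7.8, through SAP 5.1 | SAF |
| Protocol 7.2.2 | SAF |
| SAP 6.1, both Overall Total groups | FAS |
| Protocol 7.2.1, Total | not restricted |

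**3. How far could the result move?** The plan states no figure to reproduce: it is descriptive, with no sample size calculation. The only size given is about 40 patients and at most 45 (Protocol 7.5). The documents give neither an AE rate nor a rate of early loss, so the counts below are assumptions.

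Let N be the number treated, T the number with a treatment-emergent AE, and k the number of treated patients outside the FAS.

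- SAF percentage = T / N
- Lowest FAS percentage (all k had an AE) = (T − k) / (N − k)
- Highest FAS percentage (none of the k had an AE, with T ≤ N − k) = T / (N − k)

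| N | T | k | SAF | FAS, all k had an AE | FAS, none of k had an AE |
|---|---|---|---|---|---|
| 40 | 30 | 1 | 30/40 = 75.0% | 29/39 = 74.4% | 30/39 = 76.9% |
| 40 | 30 | 2 | 75.0% | 28/38 = 73.7% | 30/38 = 78.9% |
| 40 | 30 | 4 | 75.0% | 26/36 = 72.2% | 30/36 = 83.3% |
| 40 | 20 | 4 | 20/40 = 50.0% | 16/36 = 44.4% | 20/36 = 55.6% |

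The count falls by one for each excluded patient who had an event. The percentage can move either way.

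**The case against.** The strongest reply is that the operative text leaves no real doubt. SAP 5.1, 7.4.1 and 7.8, the SAF definition in SAP 6.3, the table's own safety row and Protocol 7.2.2 all lead to the SAF. Against them stands one row that also names an endpoint class this trial lacks. The general rule on percentages refers only to the respective patient set, which SAP 7.4.1 names for the primary analysis. This is right as to intent. It means the table contradicts the text and does not override it, but the contradiction remains.

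A second reply concerns the Overall Total groups. In the visible SAP analysis sections they are cited only in 7.5.2, for efficacy, where the FAS is correct; SAP 7.8.1 summarises AEs by treatment; and technical detail is left to an ADS Plan that is not available here. That narrows the point without removing it. SAP 6.1 introduces the groups for descriptive statistics generally, and Protocol 7.2.2 requires the primary endpoint to be shown by them.

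Third, the effect is probably small. Early discontinuers should attend EOT and EOS visits (flow chart footnote 4), and unscheduled measurements count (SAP 6.7). The largest swing from 75.0% needs four patients of 40 with no post-baseline EASI and no AE. This stands. Whether EASI is done at EOT and EOS cannot be checked, because that flow chart is not in the available text.

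Fourth, the word randomised in the SAF definition excludes nobody if it refers to the parent trial. This also stands: it is a wording error and adds no weight.

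**Conclusion.** The concern holds. Table 6.3: 1 assigns the primary endpoint to the wrong analysis set, and the two Overall Total definitions are wrong for any safety display. The intended set is almost certainly the SAF.

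The practical effect depends on how many treated patients lack a baseline or any post-baseline EASI, which the documents do not allow one to estimate. With one such patient among an assumed 40, the shift from 75.0% is about −0.6 or +1.9 percentage points; with four, it lies between −2.8 and +8.3. No hypothesis test is involved. It should still be corrected, because it concerns the only primary endpoint and would remove treated patients from a safety result.

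**What to change.** Three wording edits to the SAP:

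1. In Table 6.3: 1, mark the primary endpoint row under SAF. The reference to key secondary endpoints can go, since there are none.
2. In SAP 6.1, define both Overall Total groups as all patients in the analysis set of the table concerned: SAF for safety, FAS for efficacy.
3. In SAP 6.3, define the SAF as in Protocol 7.2.1, namely patients who entered this trial and received at least one dose in it, and delete the word for randomised.

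Correcting the table row alone would leave the totals wrong. The cost is a SAP revision; no data collection, analysis or protocol text changes.
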